
Leflunomide will be administered orally at an initial dose of 20 mg daily following a loading dose of 100 mg per day for the first three days of administration. For the phase I portion of the study, five daily dose levels of leflunomide may be tested (10, 20, 30, 40 or 60 mg daily) There will be no intra-patient dose escalation. The R2PD will be used as the daily dose for the phase II portion of the study. At the end of the study, all participants will receive 11 days of oral cholestyramine treatment (8 g three times daily) to reduce the plasma leflunomide levels.

Clinical Observations and Tests to be Performed:
 
Clinical observations will include tolerance as well as response to treatment. Baseline studies will include: history and physical, pulmonary function test, skeletal survey and bone marrow aspiration and biopsy (the bone marrow aspiration will be used for clinical assessment and leftover samples will be used for correlative laboratory studies), as well as a laboratory evaluation to include CBC with differential, comprehensive chemistry panel (to include LDH, magnesium, phosphorus and uric acid) and myeloma labs (serum protein electrophoresis, serum immunofixation, 24-hour urine protein electrophoresis, urine immunofixation, serum free light chains, and quantitative immunoglobulins). Clinical observation of response will take place on day 1 of each 28-day cycle. Subjects will be evaluated through clinic visits and physical exams as well as laboratory tests to include CBC with differential, comprehensive chemistry panel and myeloma labs. Blood tests will be performed at a minimum of every 28 days but may be done more frequently as clinically indicated. A skeletal survey may be repeated as clinically indicated. Patients will undergo toxicity assessment every two weeks for the first three cycles following initiation with leflunomide and will undergo, at a minimum, monthly toxicity assessments thereafter. For all phase II patients and phase I patients enrolled at the anticipated RP2D, a second bone marrow aspiration will be conducted for correlative laboratory studies on day 1 of cycle 2. Confirmation of complete response (CR), stringent complete response (sCR), and progressive disease (PD) will involve bone marrow aspiration and, for patients who have enrolled in the phase II portion, leftover samples from these bone marrow aspirations will be used

for correlative laboratory studies.
Statistical Considerations:

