5.2 Treatment cycle definition

The planned cycle length is 28 days. Leflunomide will be taken orally once daily. Missed or held doses will not be made up. The day count continues despite a hold in agent administration. Day 1 safety assessments must be reviewed prior to the initiation of the cycle. For a cycle to commence, the participant must be actively taking study agent. Windows for procedures are detailed in [Section 10](#).

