10.0 STUDY CALENDAR

Table 10 describes required procedures. All procedures may increase in frequency if clinically indicated or oriented following toxicity. Adjustments to the treatment cycle due to a hold in study agent are detailed in [Section 5.2](#).

Table 10.0 Study Activity Calendar

	Screening ^a	Cycle 1, 2, 3		Cycle 4+ ^d	End of Treatment ^e				Active Follow-Up ^j	Long Term Follow-Up ^k
		Day 1 ^b	Day 14 ^c		Day 0 ^f	Days 1-11 ^g	Day 14 ^h	Day 30 ⁱ		
Informed Consent ^l	X ^u									
Inclusion/Exclusion Criteria ^m	X									
Registration ⁿ	X ⁿ									
Medical history ^o	X									
Physical exam	X	X		X					X	
Vital signs ^p	X	X		X					X	
Adverse events assessment ^q		X	X	X	X	X			X	
Concomitant meds review	X	X		X	X				X	
ECOG status ^r	X	X		X					X	
Pregnancy test ^s	X									
TB antigen test ^t	X									
Hepatitis A, B, C testing	X ^u									
Pulmonary function test	X ^u									
Extramedullary disease survey ^v	X ^u			X ^w	X ^w				X ^w	X ^w
Skeletal survey	X ^u									
Clinical bone marrow aspiration/biopsy with research use of leftover samples	X ^{u,y}	X ^{y,z,aa}		X ^{y,z}	X ^{y,z}				X ^{y,z}	X ^{y,z}
Research bone marrow aspiration		X ^{bb}								
CBC with differential ^{cc}	X	X	X	X					X	X
Chemistry panel ^{dd}	X	X	X	X					X	X
Myeloma labs ^{ee}	X	X ^{kk}		X	X				X	X
Response assessment ^{ff}		X ^{aa}		X	X				X	X
Research blood samples ^{gg}		X	X	X	X					
Teriflunomide clinical testing ^{hh}				X		X ⁱⁱ	X ⁱⁱ			
Leflunomide administration ^{jj}		Daily								
Cholestyramine ^g					X ^g					
Survival										X ^k

a. All screening procedures to be performed within 21 days of start of study agent except informed consent, acute hepatitis panel, skeletal survey, bone marrow biopsy, and pulmonary lung function test which may occur within 30 days of start of treatment (footnote u) and except for registration which must occur within 7 days from start of treatment (footnote n).

- b. Day 1 assessments to be performed within 5 days (120 hours) prior to Day 1 drug (except footnote u for C1 only). Day 1 safety assessments must be resulted and reviewed prior to administration of agent for the cycle that is initiating. Screening assessments, if performed within this aforementioned time frame, may serve as C1D1 assessments. Note: items with footnote "aa" are not performed for C1D1; the windows for screening assessments still apply.
- c. Day 14 evaluations have +/- 3 day window.

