13.0 STATISTICAL CONSIDERATIONS

13.1 Definition of Dose-Limiting Toxicity (DLT)

A dose limiting toxicity (DLT) will be defined as any of the following toxicities that are **at least possibly related** to leflunomide and occur during cycle 1:

Any toxicity or series of toxicities resulting in:

- Fewer than 21 doses during cycle 1
- Extension of Cycle 1 > 35 days

Hematologic:

- Grade 4 neutropenia (ANC <500/mm³)
- Grade 3 or 4 febrile neutropenia
- Grade 4 thrombocytopenia (<25,000/mm³)
- Grade 3 thrombocytopenia (<50,000/mm³) with bleeding

Non- Hematologic:

- Grade 4 non-hematologic toxicity, with the following exceptions:
 - Diarrhea that resolves to G3 within 48 hours
 - Vomiting that resolves to G3 within 48 hours
 - Allergic reaction/hypersensitivity, or
 - Electrolyte/metabolic toxicity corrected to <Grade 1 or baseline within 48 hours
- Grade 3 toxicity despite maximal medical therapy lasting > 7 days
- Grade 2 or higher ALT (SGPT)/AST (SGOT)/Total Bilirubin elevation lasting > 14 days.
- Grade 3 or higher elevation of ALT (SGPT)/AST (SGOT)/Total Bilirubin of any duration.

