13.3.2 Phase I Dose Escalation

This phase I trial will employ a modified rolling six design, a more conservative version of the rolling 6 design of Skolnik, et al [1]. In this design, at most 3 patients will be under observation for DLT (in cycle 1) on the current test dose level at any time. Patients who are not evaluable for dose escalation will be replaced. Once each patient completes cycle 1 and passes without a DLT, an additional patient *may* be accrued on that dose level for up to 6 patients. Once 3 patients have completed cycle 1 with no patient at that dose level experiencing a DLT, the dose can be escalated. Up to 3 additional patients may be treated at the current dose level. Although this design does not require that 6 patients be treated, no more than 6 evaluable patients will be accrued to any dose level during the dose finding portion of this study. If at any time, the dose level has 1 documented DLT with fewer than 6 evaluable patients, accrual will continue until 6 patients are evaluable. Escalation will terminate as soon as two or more patients

experience a DLT attributable to the study treatment. MTD will be the highest dose in which $\leq 1/6$ patients experience a DLT. There will be no dose escalation within a patient. These rules are outlined in Table 13.3.2.

Table 13.3.2: Dose Escalation Rules

With DLT [^]	# Patients on Current Level		Action
	Evaluable	Evaluable + At Risk [^]	
0	0	1-2	Accrue next patient at this level*
0	0	3	Hold accrual
0	1	1-3	Accrue next patient at this level
0	1	4	Hold accrual
0	2	2-4	Accrue next patient at this level
0	2	5	Hold accrual
0	3-6	3-6	Accrue next patient at the next higher level* ^{*,+}
1	1	1-2	Accrue next patient at this level
1	1	3	Hold Accrual
1	2	2	Accrue next patient at this level
1	2	3-4	Hold accrual
1	3-5	3-5	Accrue next patient at this level
1	3-5	6	Hold accrual
1	6	6	Accrue next patient at the next higher level*
2**	any	any	Accrue next patient at next lower level (max 6)

[^]: DLT: a patient with a documented DLT
 Evaluable: a patient who is either fully evaluable for toxicity for the purpose of dose escalations or has a DLT
 At Risk: a patient who is on treatment and has not yet passed the evaluation period nor had a DLT
^{*}: During the dose-escalation portion, if higher dose level is already closed, the next lower dose will accrue to a total of 6 patients, with 2 or higher DLTs requiring further dose de-escalation.

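### The last scheduled blood tests bearing on cycle 1 may be drawn from about Day 24, and nothing requires a laboratory test at the end of the 28-day DLT window, so a silent, persistent laboratory DLT starting on Days 25-28 can be missed for escalation

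*Combined protocol and SAP*

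**What the plan says.** **DLT window.** Section 13.1 limits DLTs to toxicities at least possibly related "to leflunomide and occur during cycle 1". Section 5.2 states: "The planned cycle length is 28 days". Several DLTs are laboratory findings with no minimum duration: grade 4 neutropenia, grade 4 thrombocytopenia, and "Grade 3 or higher elevation of ALT (SGPT)/AST (SGOT)/Total Bilirubin of any duration".

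**Blood tests.** In cycles 1-3, Table 10 schedules CBC and chemistry on Day 1 and Day 14 only. Footnote c adds "Day 14 evaluations have +/- 3 day window". Footnote b says of the Day 1 set: "Day 1 assessments to be performed within 5 days (120 hours) prior to Day 1 drug (except footnote u for C1 only". It also says "Day 1 safety assessments must be resulted and reviewed prior to administration of agent for the cycle that is initiating", which a draw made five days early can satisfy. The synopsis sets the floor: "Blood tests will be performed at a minimum of every 28 days but may be done more frequently as clinically indicated".

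**Use of the result.** Section 13.3.2: "Once 3 patients have completed cycle 1 with no patient at that dose level experiencing a DLT, the dose can be escalated". Section 13.2 makes a patient evaluable for escalation after at least 75% of the drug and follow-up during cycle 1, or after a DLT. Neither section names a laboratory test that ends DLT observation.

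**The concern.** The phase I primary endpoint and the MTD rest on cycle 1 DLTs in three to six patients per dose level, so one uncounted event can change a decision. The visit allowance and the DLT window were written in different sections and do not meet at the end of cycle 1.

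A lasting abnormality that starts between the Day 14 and C2D1 draws is found at C2D1 and counts. One that starts after an early C2D1 draw is not looked for again on schedule until well into cycle 2, and by then its start cannot be placed in cycle 1. Testing when clinically indicated gives little protection, because a silent abnormality gives no indication. For lasting events the error lowers the DLT count and so favours escalation.

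**Working it through.** The plan states no figure that depends on this point, so there is none to reproduce.

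**1. Calendar.** With a 28-day cycle, C2D1 is study Day 29. Five days (120 hours) earlier is 29 - 5 = Day 24. The days left without a scheduled draw are Days 25-28, or 4/28 = 14.3% of cycle 1. Counted in hours up to the cycle 2 dose, the share is 120/672 = 17.9%. Cycle 2 Day 14 is study Day 42, so its window is Days 39-45. The gap after a Day 24 draw is 39 - 24 = 15 to 45 - 24 = 21 days.

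**2. Effect on the DLT count.** Assumptions, none of them in the documents: true DLT rate p; a share s of DLTs that are silent laboratory events; onset uniform over 28 days; every patient tested on Day 24; and events long enough that all those starting by Day 24 are seen. The observed rate is then

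p' = p × (1 - s × 4/28)

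and P(at most 1 DLT in 6) = (1 - p')^6 + 6p'(1 - p')^5.

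At p = 0.25 with full observation: 0.75^6 + 6 × 0.25 × 0.75^5 = 0.178 + 0.356 = 0.534.

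| True rate | Silent share | Observed rate | P(0 of 3) | P(at most 1 of 6) |
|---|---|---|---|---|
| 0.25 | full observation | 0.250 | 0.422 | 0.534 |
| 0.25 | 25% | 0.241 | 0.437 | 0.555 |
| 0.25 | 50% | 0.232 | 0.453 | 0.577 |
| 0.25 | 100% | 0.214 | 0.485 | 0.620 |
| 0.33 | full observation | 0.330 | 0.301 | 0.358 |
| 0.33 | 25% | 0.318 | 0.317 | 0.382 |
| 0.33 | 50% | 0.306 | 0.334 | 0.406 |
| 0.33 | 100% | 0.283 | 0.369 | 0.458 |

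Using 5/28 instead of 4/28 at a true rate of 0.30, P(at most 1 of 6) goes from 0.420 to 0.450, 0.480 and 0.542 for the same three shares.

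**3. Dependence on duration.** Blood tests are snapshots, so moving one draw also lengthens the gap after Day 14. For a silent event lasting L days with onset uniform over Days 1-28:

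- draws on Days 14 and 24 detect [min(L,14) + min(L,10)]/28;
- draws on Days 14 and 28 detect [min(L,14) + min(L,14)]/28;
- the gain from the later draw is [min(L,14) - min(L,10)]/28.

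| Duration | Days 14 + 24 | Days 14 + 28 | Gain |
|---|---|---|---|
| 5 days | 35.7% | 35.7% | 0 |
| 10 days | 71.4% | 71.4% | 0 |
| 11 days | 75.0% | 78.6% | 3.6 points |
| 13 days | 82.1% | 92.9% | 10.7 points |
| 14 days or more | 85.7% | 100% | 14.3 points |

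With a pre-dose draw on Day 29 the full gain is reached at 15 days. The figures in step 2 therefore apply only to events lasting about two weeks or longer.

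**4. Exposure.** Sections 2.2 and 8.1.4 give a half-life of about 2 weeks. A one-compartment model (an assumption) with a 14-day half-life and the three 100 mg loading doses puts the 60 mg trough at 71% of steady state on Day 24 and 78% on Day 29. Exposure is still rising in the unobserved days, but modestly.

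**The case against.** A reader might infer that DLTs in the last days of cycle 1 are missed as a rule, or that a patient tested on Day 24 is at once treated as having completed cycle 1. The documents support neither. The early draw is permitted, not required, and nothing shows how often it would be used. The notes to Table 13.3.2 keep a patient at risk until the evaluation period has passed, and Section 13.3.2 ties escalation to completion of cycle 1. The gap is in laboratory ascertainment, not in the timing of the decision.

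Three further objections have weight:

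- **Symptomatic events.** DLTs count by when they occur. Adverse event recording runs on to the EOT Day 30 visit (footnote q), so a symptomatic event on Days 25-28 that is reported later still counts. This stands, and it confines the point to silent laboratory events.
- **Silent share and duration.** Section 13.1 also lists many DLTs that would be noticed clinically. Section 6.1.1, citing the package insert, marks neutropenia and thrombocytopenia as rare and leaves liver enzyme elevation in its infrequent group. The silent share may be small, and brief events show no net gain from a later draw. This limits the size; it does not close the gap.
- **Backstops.** The RP2D may be set below the MTD on cumulative toxicity, the Protocol Management Team monitors safety, and tests may be repeated more often after toxicity. A lasting abnormality would probably be found in cycle 2 and could still inform the phase II dose. It would not enter the cycle 1 count that drives escalation and the MTD.

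**Conclusion.** The point holds in a limited form. The 120-hour allowance, the cycle 1 DLT definition and the lack of an end-of-cycle test together let a silent laboratory DLT that starts on Days 25-28 and persists go uncounted.

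At a true DLT rate of 25%, the chance of at most 1 DLT in 6 rises by 2.1, 4.3 or 8.6 percentage points for a silent share of 25%, 50% or 100%. This requires that every patient is tested on Day 24, that onset is uniform and that events last about two weeks or longer. The effect is little or none for events of about 10 days or less, and the gap disappears if blood is drawn on the day. These are ranges under assumptions, not predictions. It might be tempting to quote the 100% row as the expected effect, but nothing in the documents suggests that all DLTs would be silent and long-lasting.

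This is a cheap improvement to how the primary endpoint is ascertained. It is not an error that invalidates the phase I design.

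**What to change.** Reconcile footnote b of Table 10 with Sections 13.1, 13.2 and 13.3.2. For phase I only, add to footnote b:

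- The CBC and chemistry panel that complete DLT observation for cycle 1 are drawn on cycle 1 Day 28, or on C2D1 before the dose. If drawn earlier, they are repeated then.
- A patient is not counted in Table 13.3.2 as evaluable without a DLT until those results, and an adverse event review covering the whole of cycle 1, are complete.

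Keep the 5-day allowance for all other cycles and for phase II. The change retimes a draw that is already scheduled. It adds no visit or test type and sets no dose or treatment rule. The cost is less scheduling flexibility, or an occasional repeat blood draw, at one visit in the 12-18 expected phase I patients.

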Following the phase I trial, a single arm phase II trial will be conducted using a Simon Two-Stage Optimal Design [2, 3] to evaluate the anti-myeloma activity of leflunomide, when given as a single agent, as assessed by overall response rate (ORR). The phase II portion of the study is expected to enroll a minimum of 19 and a maximum of 39 patients. The sample size is based on the desire to discriminate a promising ORR of 30% from a disappointing response rate of 15% using a type I error rate of 0.10 and power of 80%.

Patients will be treated in planned 28-day treatment cycles until disease progression, unacceptable toxicity, or other criteria for removal from study treatment are satisfied. Patients will undergo monthly evaluation for response using the International Myeloma Working Group (IMWG) criteria.

Endpoints:

Phase I: The primary endpoint is toxicity. Toxicity will be graded according to the NCI-Common Terminology Criteria for Adverse Events version 4.03. Dose limiting toxicity (DLT) is defined in [Section 13.1](#) of the protocol.

Phase II: The primary endpoint is response. Response will be categorized using the IMWG response criteria for multiple myeloma [37, 38]. The response categories and criteria are summarized in Table 11.2 of the protocol.

Sample Size:

The expected phase I sample size is 12-18 patients; allowing for 6 patients to replace invaluable/ineligible patients. The expected phase II sample size is 19-39 patients. It is anticipated that the 6 patients from the phase I portion who are treated at the R2PD will be included in the sample size for the phase II portion (phase I/II participants).

Estimated Duration of the Study

With an expected accrual rate of approximately 1 patient enrolled per month, the phase I portion of the trial is expected to complete accrual in 12-18 months. The phase II portion is expected to accrue 2 patients per month, with completion in 17 months. The expected maximum duration of therapy is 24 months. The total study is expected to last a maximum of (18+17+24) 59 months or approximately 5 years.

Summary of Subject Eligibility Criteria:

Inclusion Criteria:

Participants must meet the following criteria on screening examination to be eligible to participate in the study:

- All subjects must have the ability to understand and the willingness to sign a written informed consent.
- Patients must be age ≥ 18 years.
- Patients must have a life expectancy of > 3 months.

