- l. Informed consent process to be fully documented: e.g. prospective participant had sufficient time for deliberation, all questions were answered, treatment options provided by MD, full study reviewed including risks, and a copy of signed consent given to participant.
- m. Inclusion/exclusion criteria are detailed in [Section 3](#).
- n. See [Section 4.3](#) for slot reservation and registration process. Treatment must begin within 7 days of registration. Documentation providing Investigator's confirmation that all eligibility criteria are met must be available prior to registration.
- o. Medical history to include review treatment history for myeloma, medical history pertaining to eligibility, and demographic information.
- p. Vital signs: Weight, heart rate, blood pressure, respiration rate, temp. Height required only at baseline.
- q. Adverse event (AE) reporting begins for events that occur after start of study agent. AE recording and reporting will continue until the completion of the EOT Day 30 visit or until resolution or stabilization of any serious AE occurring before the completion the EOT Day 30 assessments, which every occurs later.
- r. See Appendix A for ECOG performance status criteria.
- s. Serum or urine pregnancy test for women of child bearing potential only.

- t. T-Spot or other TB antigen test.
- u. Consent, acute hepatitis panel, skeletal survey, bone marrow biopsy, bone marrow aspiration, and pulmonary lung function test to be completed within 30 days prior to registration.
- v. Extramedullary disease survey required at screening for all participants with known or suspected extra-medullary disease. May include CT scan of the abdomen/pelvis, CT or x-ray of the chest, ultrasound of the liver/spleen or abdomen. Technique used at screening/baseline (if applicable) should be used throughout the study and include tumor measurements.
- w. Extramedullary disease survey required after screening/baseline only in patients with extramedullary disease present at screening/baseline. To occur every 12 weeks or upon clinical suspicion of progressive disease.
- x. Skeletal survey (including skull, all long bones, pelvis and chest) with tumor measurements (if plasmacytomas are present). To be performed at baseline/screening and when clinically indicated.

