11.2 Phase II/Primary Endpoint: Response

The primary endpoint is response. Response will be categorized using the IMWG response criteria for multiple myeloma [37, 38]. Table 11.2 summarizes the categories and criteria.

Table 11.2 Response Criteria

Response Category	Response Criteria
Complete response (CR)*	Negative immunofixation of serum & urine, AND Disappearance of any soft tissue plasmacytomas, AND < 5% plasma cells in bone marrow
Stringent complete response (sCR)*	CR (as defined above) PLUS: Normal FLC ratio, AND Absence of clonal cells in bone marrow by immunohistochemistry or immunofluorescence
Very good partial response (VGPR)**	Serum and urine M-component detectable by immunofixation but not on electrophoresis, OR ≥ 90% reduction in serum M-component plus urine M-component < 100mg per 24h
Partial response (PR)**	≥ 50% reduction of serum M protein and reduction in 24h urinary M protein by ≥ 90% or to < 200mg per 24h If serum and urine M protein are unmeasurable, a ≥ 50% decrease in the difference between involved and unininvolved FLC levels is required in place of the M protein response criteria If serum and urine M protein are unmeasurable, AND serum free light assay is also unmeasurable, a ≥ 50% reduction in bone marrow plasma cells is required in place of M protein, provided baseline percentage was ≥ 30%. In addition to the above criteria, if present at baseline, ≥ 50% reduction in the size of soft tissue plasmacytomas is also required
Minimal Response	• 25% but ≤ 49% reduction of serum M protein and reduction in 24-hour urine M-protein by 50 to 89% which still exceeds 200 mg per 24 hr

Response Category	Response Criteria
(MR)**, ***	
 In addition to the above criteria, if present at baseline, 25-49% reduction in the size of soft tissue plasmacytomas is also required No increase in size or number of lytic bone lesions (development of compression fracture does not exclude response)
Stable disease (SD)**	Not meeting criteria for CR, VGPR, PR, or PD

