Progressive disease (PD)**	
Increase of 25% from lowest response value in any one or more of the following:
 
 Serum M-component (absolute increase must be ≥ 0.5 g/100ml), and/or Urine M-component (absolute increase must be ≥ 200mg per 24h), and/or Only in patients without measurable serum and urine M-protein levels: 
 The difference between involved and unininvolved FLC levels (absolute increase must be > 10mg/dl) Bone marrow plasma cell percentage (absolute % must be $\geq 10\%$) Definite development of new bone lesions or soft tissue plasmacytomas OR definite increase in the size of existing bone lesions or soft tissue plasmacytomas Development of hypercalcemia (corrected serum calcium > 11.5mg/100ml) that can be attributed solely to the plasma cell proliferative disorder

* Confirmation with bone marrow assessment is required for CR and sCR. Only a single bone marrow assessment is needed. CR and sCR require no known evidence of progressive or new bone lesions if radiographic studies are performed.

** The following response categories: VGPR, PR, MR, SD, and PD require 2 consecutive assessments made at any time before the institution of any new therapy. VGPR, PR, MR, and SD require no known evidence of progressive or new bone lesions if radiographic studies are performed. The second assessment might be at the time of a planned assessment or earlier, based on the judgement of the treating physician.

*** Based on the recommendations in Rajkumar et al. [38], MR will be reported separately and will be distinguished from PR or better.

11.3 Phase II/Secondary Endpoints:

Best Overall Response:

Based on the International Myeloma Working Group (IMWG) criteria, best overall response is the best response (sCR/CR/VGPR or PR) recorded from the start of treatment until disease progression. Confirmation of sCR/CR/VGPR or PR assessed by IMWG criteria.

Response Duration:

Defined as the time interval from the date of first documented response (sCR/CR/VGPR or PR) to documented disease progression or death whichever occurs first.

Clinical Benefit Response:

Based on the International Myeloma Working Group (IMWG) criteria, clinical benefit response is the best response (sCR/CR/VGPR/PR/MR or SD) recorded from start of treatment until disease progression. Confirmation of sCR/CR/VGPR/PR/MR or SD assessed by IMWG criteria.

Overall Survival:

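### Plasmacytoma response is part of PR and CR, but no scan is triggered by suspected response, no rule covers scoring between 12-weekly scans, and the VGPR row omits the condition

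*Combined protocol and SAP*

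**What the plan says.** **Assessment interval.** Protocol Synopsis, Study Design: "Patients will undergo monthly evaluation for response using the International Myeloma Working Group (IMWG) criteria".

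**Response criteria (Section 11.2, Table 11.2).** If plasmacytomas were present at baseline, PR carries an added condition: "≥ 50% reduction in the size of soft tissue plasmacytomas is also required". MR has the parallel condition "25-49% reduction in the size of soft tissue plasmacytomas is also required". CR requires soft tissue plasmacytomas to have disappeared. The VGPR row offers two routes. One is "Serum and urine M-component detectable by immunofixation but not on electrophoresis"; the other is a serum fall of at least 90% with urine M-component under 100 mg per 24 h. Neither route mentions plasmacytomas.

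**Confirmation (Table 11.2 footnotes).** VGPR, PR, MR, SD and "PD require 2 consecutive assessments made at any time before the institution of any new therapy". For CR and sCR, a single marrow assessment is enough. No footnote says how many surveys the plasmacytoma component needs.

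**Imaging (Section 10, Table 10).** Footnote w: "Extramedullary disease survey required after screening/baseline only in patients with extramedullary disease present at screening/baseline". Its timing is "To occur every 12 weeks or upon clinical suspicion of progressive disease". By contrast, footnote z calls for a marrow examination to confirm suspected CR, sCR or PD.

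**Use of the result (Sections 11.3 and 13.3).** Best response up to progression is what counts. CR, sCR, VGPR and PR make up the ORR. Stage 1 stops at 3 or fewer responders of 19; success needs 9 or more of 39.

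**The concern.** A component of the phase II primary endpoint is measured less often than the endpoint is scored, and the plan does not say what to do in between. One assessor may wait for the next scan, another may carry the last scan forward, and a third may score PR on M-protein alone. The first approach can lose or delay responses; the other two can credit responses whose lesion component was never shown. In a single-arm trial whose stage 1 decision separates 3 from 4 responders, one patient scored differently can change the outcome.

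The VGPR row raises a separate problem that does not depend on scan timing. A higher response category carries fewer conditions than the one below it, so the same unchanged lesion blocks a PR but not a VGPR. Both categories count equally in the ORR.

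The date of first response is affected too, and so is response duration, wherever credit waits for a scan.

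**Working it through.** **1. Schedule.** With 28-day cycles, assessments fall at weeks 4, 8, 12, 16, 20, 24 and so on. Scheduled surveys fall at about weeks 12, 24, 36 and so on. Two of every three assessments (weeks 4, 8, 16, 20, ...) therefore have no scheduled lesion measurement.

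**2. What can happen to an M-protein PR in a patient with a baseline plasmacytoma:**

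- *Begins by week 4 and ends before week 12.* The only scheduled scan is the baseline one, which cannot show shrinkage. The response goes uncredited, or is credited with no post-baseline measurement. A scan prompted by suspected progression shows the lesion at progression, not at response.
- *Begins by week 4 and lasts to week 12.* The scan can support it. Credit is delayed by up to 12 − 4 = 8 weeks, and measured response duration shortens by the same amount if response is dated from the scan.
- *First seen at week 16 or 20.* The latest scheduled scan is from week 12. PR is either scored on that older scan or waits for week 24.

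**3. VGPR row against PR row.** Take a patient whose plasmacytoma has not changed, and assume the urine criteria for the category are met:

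| Serum M-protein fall | Category as written | In ORR? |
|---|---|---|
| at least 90% | VGPR (no lesion condition) | yes |
| 60-89% | not PR (lesion condition fails) and outside the MR range, so SD | no |

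**4. The plan's own design figures.** With b(n, x, p) the binomial probability:

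- Early stopping = Σ b(19, x, p) for x = 0 to 3.
- Probability of success = Σ b(19, x, p) × P(Bin(20, p) ≥ 9 − x) for x = 4 to 19.

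At p = 0.15, early stopping is 0.684 (stated 0.68) and type I error 0.097 (limit 0.10). At p = 0.30, power is 0.803 (stated 0.80). The design reproduces and is not in question.

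**5. Illustration of lost responses.** Let f be the share of patients with extramedullary disease and m the share of their responses left uncredited. Both are assumptions; the documents give neither. These patients are taken to have the same underlying 30% response rate, so the observed rate is 0.30 × (1 − f × m).

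| f | m | Observed ORR | Power |
|---|---|---|---|
| 0 | – | 0.300 | 0.803 |
| 5% | 50% | 0.2925 | 0.777 |
| 5% | 100% | 0.285 | 0.749 |
| 10% | 50% | 0.285 | 0.749 |
| 10% | 100% | 0.270 | 0.687 |

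**6. Illustration of over-credited responses.** If unverified responses are credited to a share g of these patients, the null rate becomes 0.15 + f × g. With f = 10% and g = 5%, 10% or 20%, it is 0.155, 0.16 or 0.17, and type I error rises from 0.097 to 0.114, 0.131 or 0.171.

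**The case against.** **The plan does not forbid extra scans.** Section 10 lets any procedure be done more often if clinically indicated, and footnote x allows skeletal surveys with plasmacytoma measurements on the same basis. This stands, and it rules out saying that these patients cannot be scored. But both provisions are discretionary, and neither gives a scoring rule.

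**A reader might infer that PR cannot be confirmed before about week 24,** because two consecutive assessments would need two scans. The text does not establish this. The confirmation footnote lets the second assessment fall earlier at the treating physician's judgement. It also applies its bone-lesion condition only where radiographic studies are done, so it envisages assessments without imaging. Week 24 is one reading among several, and the ambiguity itself is what needs settling.

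**A reader might infer that these responses are simply lost.** Best response up to progression is what counts, and Section 5.9 continues monthly assessment after treatment for patients who have not progressed. A response that persists to a scan is credited late. The overall survival of 6 to 10 months quoted in Section 2.1 is no evidence of loss: it describes patients with more than 3 prior regimens, whereas this trial admits those with at least 3, and survival does not show how long responders remain assessable.

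**MR changes no planned rate.** It lies outside the ORR, and clinical benefit counts MR and SD alike. This is correct, so the point rests on PR and CR.

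**Table 11.2 only summarises the cited criteria,** which may treat VGPR differently. That cannot be checked from the documents. What stands is that the table, as the plan's operative text, ranks VGPR above PR but asks less of it.

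**Conclusion.** The point holds, within limits. For patients with baseline plasmacytomas, Table 11.2, the two-assessment rule and footnote w do not fit together. The plan supplies neither a survey trigger for suspected response nor a rule for scoring between scans. The VGPR row is inconsistent with the CR, PR and MR rows whatever the scan timing.

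The size is unknown. Only patients with extramedullary disease at baseline are affected, and their share is not given. Power of about 0.78-0.75 (5% share) or 0.75-0.69 (10% share) assumes that half to all of their responses go uncredited. The all-lost end is a ceiling, since persistent PRs are credited late and VGPR as written needs no scan. Error in the other direction, towards a higher type I error, is equally possible, and no net bias can be claimed. A reader might take the power figures as an estimate of loss; they only show sensitivity. The case for change is that the primary endpoint can be misclassified in either direction by following the plan as written, and that this is cheap to prevent.

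**What to change.** Settle the following before phase II responses are adjudicated:

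1. **Table 11.2 footnotes.** State that the plasmacytoma component of CR, VGPR or PR needs one qualifying survey, done at or after the first qualifying M-protein assessment. The M-protein part of VGPR and PR is still confirmed on two consecutive assessments. This mirrors the single-marrow rule already in place for CR and sCR.
2. **Table 10, footnote w.** Add first suspected response as a survey trigger beside suspected progression. Use the scheduled 12-week survey if it is close in time, with a stated window for what counts as close. Leave the 12-week schedule otherwise unchanged: restarting the clock at a week-4 response would move the next scan from week 12 to week 16 and could itself delay credit.
3. **VGPR row.** Reconcile it with the PR row, so that VGPR requires at least the PR plasmacytoma condition when lesions were present at baseline.

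The cost is wording in one table and one footnote, plus an occasional earlier or additional scan in patients with baseline extramedullary disease. A few serologic VGPRs may no longer count as responses. The sample size and decision boundaries stay as they are.
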